MedDRA	Medical Dictionary for Regulatory Activities
MRT	Mean residence time of the drug in the body
NA	Not available
nAb	Neutralizing antibody
NCS	Not clinically significant
NK	Not known
PD	Pharmacodynamic
PDS	Protocol Deviation Specification
PK	Pharmacokinetic
PKS	Pharmacokinetic analysis set
QT	The QT interval is measured from the beginning of the QRS complex to the end of the T wave
QTc	corrected QT interval
QTcB	QT corrected using Bazzett's formula
QTcF	QT corrected using Fridericia's formula
SAD	Single ascending dose
SAE	Serious adverse event
SAP	Statistical Analysis Plan
SD	Standard deviation
SOC	System Organ Class
$t_{\frac{1}{2}}$	Terminal half-life associated with the terminal phase
TEAE	Treatment-emergent adverse event
$t_{\text{Emax,obs}}$	Time to reach maximum observed effect

Abbreviation / Acronym	Definition / Expansion
t_{max}	Time to maximum observed concentration
V_z	Volume of distribution during the terminal phase
V_{ss}	Steady state volume of distribution following IV dosing
WHO-DD	World Health Organisation - Drug Dictionary
λ_z	Terminal elimination rate constant

1 INTRODUCTION

XTMAB-16 is a chimeric human-murine IgG1κ anti-TNFα monoclonal antibody. The final dosage form is a sterile, white, lyophilized powder for intravenous (IV) infusion. Participants assigned to active treatment will receive a single dose of XTMAB-16 at a volume of 250 mL via IV infusion over 2 hours. The total dose received will be either 2 or 4 mg/kg, depending on treatment assignment.

Placebo will be the same formulation as the active treatment but without XTMAB-16. Participants assigned to placebo will receive a single dose of placebo at a volume of 250 mL via IV infusion over 2 hours.

This is a single-center, randomized, double-blind, placebo-controlled, first-in-human (FIH), single IV infusion of sequential ascending doses of XTMAB-16 in normal healthy male and female participants.

A total of 24 normal healthy adult participants will be enrolled and assigned into 2 treatment cohorts with 12 participants (9 on XTMAB-16 and 3 on placebo) in each cohort. Participants will receive a single IV infusion of 2 or 4 mg/kg of XTMAB-16 or placebo on Day 1.

The Statistical Analysis Plan (SAP) details the statistical methodology to be used in analyzing study data related to safety, pharmacokinetic (PK) and outlines the statistical programming specifications for the Tables, Listings and Figures (TLFs).

The analyses described in this SAP are based upon the following study documents:

- Study Protocol, Version 4.0, Amendment 3 (May 28, 2021)

This SAP will be finalized prior to database lock. Any changes after the finalization of this SAP will be documented in Statistical Method Modification Form.

2 STUDY OBJECTIVES

2.1 Primary Objective(s)

To evaluate the safety, tolerability, immunogenicity, PK, and selected clinical biomarkers after a single intravenous infusion of XTMAB-16 at 2 and 4 mg/kg doses in normal healthy participants.

2.2 Secondary Objective(s)

Not Applicable.

2.3 Exploratory Objective(s)

[figure not shown]
Not Applicable.

3 INVESTIGATIONAL PLAN

3.1 Overall Study Design and Plan

This is a single-center, randomized, double-blind, placebo-controlled, first-in-human (FIH), single IV infusion of sequential ascending doses of XTMAB-16 in normal healthy male and female participants.

A total of 24 normal healthy adult participants will be enrolled and assigned into 2 treatment cohorts with 12 participants (9 on XTMAB-16 and 3 on placebo) in each cohort as shown in [Table 1](#). Participants will receive a single IV infusion of 2 or 4 mg/kg of XTMAB-16 or placebo on Day 1.

Figure 3-1 Study Design

Abbreviations: FU = follow-up.

Table 1 Dose Cohorts

Cohort	Dose	Escalation Factor	XTMAB-16	Placebo ^a	Total
1	2 mg/kg	-	9	3	12
2	4 mg/kg	2 x	9	3	12

^a The matching placebo will be identical to the XTMAB-16 in terms of volume and infusion duration.

For all cohorts, a sentinel group of 2 participants (1 assigned to XTMAB-16 and 1 assigned to placebo) will be dosed at least 48 hours before the remaining participants in the same cohort. To maintain the treatment blind, study treatment will be prepared by an unblinded pharmacist according to the treatment assignment who will appropriately label the study drug for administration in a way that maintains the treatment blind to clinical research unit (CRU) staff and the participant.

After blinded review of the available safety and laboratory data of the sentinel group by the Principal Investigator (PI), if no notable safety signals are identified, the remaining participants within the same cohort will be dosed. Participants within a cohort should be dosed at least 1 hour apart. If there are no safety concerns, the participants in Cohort 2 will receive XTMAB-16 after at least 14 to 21 days clinical assessment of the participants at Cohort 1.

After a screening period of up to 28 days, participants will be admitted to the CRU on Day -2 for COVID-19 testing and baseline procedures. After confirmation of eligibility, participants will be randomly assigned to treatment (1:1 XTMAB-16 to placebo for sentinel cohort, 4:1 for remaining participants) and administered study drug on Day 1. Participants will remain at the CRU through Day 8 for PK, biomarkers, anti-drug antibody (ADA), and safety assessments, and will be discharged on Day 8 once all procedures for that day have been completed. Participants will return to the CRU on Days 15, 29, 43, 57, and 71 (End of Study/safety follow-up).

Safety assessments will include adverse events (AEs), safety laboratory assessments, vital signs, 12-lead electrocardiogram (ECG), and physical examination. Samples for PK, Pharmacodynamic (PD) and immunogenicity will be collected and analysis will also be completed during the course of this study.

3.1.1 Randomization and Blinding

In this study participants will be randomly assigned to treatment (XTMAB-16 or placebo) and treatment assignment will be double-blind: participants and all study staff will be blind to participant treatment assignment for the duration of the study except as specified.

The randomization schedule will be generated by an unblinded statistician (third-party unblinded) and will be provided to the CRU pharmacist prior to the start of this study. All randomization information will be stored in a secured area, accessible only by authorized personnel.

The Investigator (or designee) will assign participant numbers as participants are screened for the study. In accordance with the randomization numbers, the participant will receive the study treatment regimen assigned to the corresponding randomization number.

To maintain the treatment blind, an otherwise uninvolved, third-party unblinded CRU staff member (e.g., pharmacist) will be responsible for the preparation and dispensing of all study treatment according to the randomization schedule and assigned treatment for the individual participant. The unblinded pharmacist will have no contact with study participants and will ensure that no treatment assignment information is transmitted to study unit staff except as defined in next Section.

3.1.2 Unblinding Procedure

Treatment assignment will be double-blind. Investigators, participants, CRO, and sponsor will be blinded throughout the study. Actual treatment assignment will be available after the occurrence of database lock for the purpose of performing statistical analyses of clinical trial data.

3.1.3 Dose Escalation

For all cohorts, a sentinel group of 2 participants (1 assigned to XTMAB-16 and 1 assigned to placebo) will be dosed at least 48 hours before the remaining participants in the same cohort. After blinded review of the available safety and laboratory data by the PI, if no notable safety signals are identified, the remaining participants within the same cohort will be dosed. Participants within a cohort should be dosed at least 1 hour apart.

As XTMAB-16 is a TNF α inhibitor, which have well-characterized clinical safety profiles, it can be given to participants in the 4 mg/kg dose group after 14 to 21 days clinical assessment of the participants at 2 mg/kg dose group, unless safety concerns arise.

Dose escalation will be stopped as soon as safety signals or risks are identified or anticipated, based on:

- Number of abnormal and clinically significant safety laboratory results
- Number of serious Adverse Events (AEs), Serious Adverse Events (SAEs) and/or treatment-emergent AEs (TEAEs) with severity/intensity high enough for a meaningful decision
- Proportion of TEAEs of the same type high enough to justify the decision.

The severity rating is adapted to healthy participants, taking into account event characteristics such as type, deleterious potential, occurrence, progression, and monitorability. A solitary SAE occurrence is not by itself a criterion for making a decision (assessment depends on the nature of the reported event).

A decision to proceed from dose “n” to the next higher “n+1” dose will be made jointly by the Sponsor and the Investigator based on a preliminary Investigator blinded safety report inclusive of the 12 participants in dose level cohort “n”. The relevant data for this decision should be, at a minimum, AEs, liver and kidney function tests, ECG, blood pressure, and heart rate.

For safety purposes, the treatment of a specific participant may be unblinded before the next dose level is administered, after mutual agreement between the Sponsor and the Investigator.

An unscheduled PK sample collection and analysis may be performed to support the clinical safety assessment, if needed in the event of a safety signal of concern.

Depending on the tolerability profile and safety laboratory results observed in the dose level cohort “n,” one of the following decisions will be made for cohort “n+1”:

- Dose escalation may continue as scheduled.
- A higher intermediate dose between the current dose (“n”) and the next planned dose (“n+1”) may be administered to the next cohort.
- A lower intermediate dose between the current dose (“n”) and the previous dose (“n-1”) may be administered to the next cohort, including the possibility of administering a dose lower than the starting dose.
- The study may be stopped as per stopping rule mentioned in protocol.

3.2 Endpoints and Associated Variables

3.2.1 Primary Endpoints

Safety and Tolerability

- The incidence of treatment-emergent adverse events (TEAEs) and serious adverse events (SAEs).
- Observed values and change from Baseline in safety laboratory tests (hematology, clinical chemistry, urinalysis) by visit.
- Observed values and change from Baseline in ECG parameters by visit.
- Time-matched Baseline and 50-hr post dose digital ECG parameters monitoring.
- Observed values and change from Baseline in vital signs.

Immunogenicity

- Number and percentage of participants by cohort who test positive for XTMAB-16 anti-drug antibody (ADA) at Baseline, Day 29, Day 57, and Day 71
- Number and percentage of participants by cohort who test positive for XTMAB-16 neutralizing antibody (nAb) at Baseline, Day 29, Day 57, and Day 71

Biomarkers

Absolute and percent change from Baseline in the following biomarkers:

- Angiotensin converting enzyme (ACE)
- soluble IL-2 receptor (sIL-2R)
- Interleukin 6 (IL-6)
- soluble TNF α (sTNF α)

Other relevant biomarkers may be assessed to better understand PK/PD relationships.

3.2.2 Secondary Endpoints

Not Applicable

Pharmacokinetics

Serum PK of XTMAB-16 will be assessed after single dose administration of XTMAB-16 as below:

- C_{max} : Maximum observed XTMAB-16 serum concentration
- C_T : XTMAB-16 serum concentration at the end of drug infusion
- t_{max} : Time to maximum observed XTMAB-16 concentration
- AUC_{0-inf} : Area under the XTMAB-16 concentration-time curve from time zero extrapolated to infinity
- AUC_{0-last} : Area under the XTMAB-16 concentration-time curve from time zero to the last quantifiable concentration
- CL : Systemic clearance after IV dosing
- λ_z : Terminal elimination rate constant
- $t_{1/2}$: Terminal elimination half-life calculated as: $\ln 2 / \lambda_z$
- V_z : Volume of distribution during the terminal phase calculated as: $Dose / (\lambda_z \cdot AUC_{0-inf})$
- V_{ss} : Steady state volume of distribution following IV dosing calculated as: $MRT \cdot CL$
- MRT : Mean residence time

*Dose normalized C_{max} , AUC_{0-t} , and AUC_{0-inf} will be also calculated

3.2.3 Exploratory Endpoints

Not Applicable

3.2.4 Safety Variables

- Vital signs (supine blood pressure [BP] and pulse, tympanic (ear), oral and temporal body temperature, respiratory rate)
- 12-lead electrocardiograms (ECG): P wave, QRS complex, U wave, QRS duration, QT interval, QTcF, T wave, ST segment, RR interval, PR interval, and qualitative results.
- Telemetry
- Clinical laboratory tests (hematology, biochemistry, urinalysis, Virology, Urine Drug abuse Screening, Serum Pregnancy Test)
- Adverse event (AE) assessments
- Physical examinations

3.2.5 Pharmacodynamic Variables

Not Applicable

3.2.6 Immunogenicity Variables

Immunogenicity testing XTMAB-16 of ADA and nAb using designated serum samples from each participant is planned to be conducted.

An individual sample result will be designated “antibody positive” based on both positive screening and confirmation assay results (i.e., confirmed positive result), and otherwise will be deemed “antibody negative” or “inconclusive.” The titer assay will be performed for antibody-positive samples. For (anti-drug XTMAB-16 antibodies) positive samples, the presence of neutralizing antibodies may be determined using the (anti-drug XTMAB-16 antibodies) neutralizing assays.

Study participants will be given “positive” status if they have at least one antibody positive sample result at any time post baseline (during either the Treatment and Observation Period or the Safety Follow-up Period). A study participant will be given “negative” status if all evaluated immunogenicity sample results during the Postbaseline Period are antibody negative.

The antibody response in antibody-positive participants can be further classified by the following criteria:

- “Treatment-induced”: Has at least one antibody positive sample at any time after treatment (for participants with antibody-negative status at Baseline)
- “Treatment-boosted”: Has at least one antibody-positive sample at any time after treatment with a titer of four-fold or greater compared to Baseline (for participants with antibody-positive status at Baseline)

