4.12 Other Analyses

4.12.1 Immunogenicity

If ADA or nAb are detected, a direct link model may be used to describe the relationship between the serum concentration of XTMAB-16 and ADA or nAb levels, as AUC and time point concentration measurements to explore the time-dependence.

If ADA or nAb are detected, a summary table of PK parameter by ADA and nAb status (Positive or Negative) will be provided using PK analysis set.

Anti-drug antibodies and nAb at each sampling time will be summarized with descriptive statistics (N, mean, SD, coefficient of variation [CV], geometric mean, geometric CV, median, minimum, and maximum) for each dose cohort and Day.

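### Participant-level ADA status ignores the baseline result, so the PK-by-ADA table can mix pre-existing antibody with antibody that arose after dosing

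*SAP*

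**What the plan says.** SAP 3.2.6 calls a sample antibody-positive when both the screening and the confirmatory assay are positive, and positive samples are titred. It then sets participant status from post-baseline samples alone. A participant is positive "if they have at least one antibody positive sample result at any time post baseline" and negative "if all evaluated immunogenicity sample results during the Postbaseline Period are antibody negative".

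The same section goes on: "The antibody response in antibody-positive participants can be further classified by the following criteria". Treatment-induced applies to participants who were negative at Baseline. Treatment-boosted applies to those positive at Baseline and requires a positive sample "at any time after treatment with a titer of four-fold or greater compared to Baseline".

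The endpoint in SAP 3.2.1 is a count and percentage, by cohort, of those who "test positive for XTMAB-16 anti-drug antibody (ADA) at Baseline, Day 29, Day 57, and Day 71", with a matching line for nAb.

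SAP 4.12.1 lists three things: a possible direct-link model of drug concentration against ADA or nAb levels; descriptive statistics by dose cohort and day; and a third item, conditional on either kind of antibody being found: "a summary table of PK parameter by ADA and nAb status (Positive or Negative) will be provided using PK analysis set". The induced and boosted classes appear in none of them.

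**The concern.** The objective covers immunogenicity after a single infusion, and ADA is listed under the primary endpoints. The natural question is what antibody response follows dosing. A participant-level status that takes no account of baseline cannot answer that, because it gives one label to a new response and to antibody that was there all along.

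The SAP foresees antibody-positive participants at Baseline: it tests for them and writes a boosting rule. It then leaves those who are not boosted without a class and makes the classification optional.

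The place where this matters is the PK-by-ADA table. If exposure differs between its two rows, a reader cannot tell whether the difference goes with pre-existing antibody or with antibody that appeared after dosing. With nine active participants per dose, one person can change the picture.

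**Working it through.** The plan states no ADA rate, so there is no figure of its own to reproduce. The check has four parts.

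**1. Outcomes under the SAP 3.2.6 rules**

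| Baseline | After dosing | Status | Class |
|---|---|---|---|
| Negative | All negative | Negative | none needed |
| Negative | Any positive | Positive | Induced |
| Positive | All negative | Negative | none needed |
| Positive | Positive, titre at least 4 times Baseline | Positive | Boosted |
| Positive | Positive, titre under 4 times Baseline | Positive | **none** |

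Only the last line is a gap. It includes participants whose titre rises by less than four-fold as well as those whose titre does not change.

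**2. Denominators**

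From SAP 3.1, each cohort has a sentinel pair (1 active, 1 placebo) and 10 further participants at 4:1 (8 active, 2 placebo). That gives 9 active and 3 placebo, which agrees with SAP Table 1. Over two cohorts there are 18 active and 6 placebo participants. SAP 4.5 leaves placebo out of PK summaries, so the PK-by-ADA table holds at most 18.

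**3. Size of the shift**

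Let t be the number of induced or boosted participants, b the number with pre-existing antibody that persists without boosting, and n the group size. The ever-positive rate under the SAP status is (t + b)/n. The treatment-emergent rate is t/n. The difference is b/n.

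- One such participant in a dose group: 1/9 = 11.1 points.
- One across all active participants: 1/18 = 5.6 points.
- If the cohort denominator includes placebo: 1/12 = 8.3 points.

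| n | t | b | SAP status | Treatment-emergent | Share of positives not emergent, b/(t + b) |
|---|---|---|---|---|---|
| 9 | 1 | 1 | 2/9 = 22.2% | 1/9 = 11.1% | 1/2 |
| 9 | 2 | 1 | 3/9 = 33.3% | 2/9 = 22.2% | 1/3 |
| 18 | 2 | 1 | 3/18 = 16.7% | 2/18 = 11.1% | 1/3 |
| any | t | 0 | t/n | t/n | 0 |

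SAP 4.10.2 gives no descriptive statistics for fewer than three PK values. With t = 2 and b = 1, the one pre-existing positive is what brings the positive row up to three.

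**4. How likely is b to be above zero?**

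The documents give no baseline prevalence, so p is an assumption, shown over a range. The chance of at least one baseline-positive participant among n is 1 − (1 − p)^n.

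| Assumed p | n = 9 | n = 18 |
|---|---|---|
| 0% | 0% | 0% |
| 2% | 17% | 30% |
| 5% | 37% | 60% |
| 10% | 61% | 85% |
| 20% | 87% | 98% |

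These are upper bounds on the chance that the gap matters, because the participant must also stay positive after dosing and not be boosted.

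**The case against.** A reader might infer that the plan inflates ADA incidence. The documents do not support that. The stated endpoint is positivity at each named visit, with Baseline as one of them, so a pre-existing positive is visible and is counted as defined. No output listed in SAP 4.12.1 reports an overall ever-positive rate. This part of the objection stands. Its limit is that by-visit counts do not link individuals: 1/9 at Baseline and 2/9 at Day 71 fits one new positive, and equally fits two new positives with the first turned negative.

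A reader might also infer that the PK table is contaminated and could hide an effect of ADA on clearance. That is too strong. The table can be read as asking whether exposure differs when antibody is present, and antibody present before dosing may itself affect exposure, so positive is a defensible label. This counts against moving such participants in with the negatives, which could itself mask an ADA effect. It does not justify one combined row, which cannot show which kind of antibody goes with a PK difference.

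There are real safeguards. Positive samples are titred, samples come from all participants including placebo, and the optional direct-link model uses levels over time. The output shells are not among the documents and may already contain a finer split. The consequence is also limited: Protocol 9.1 plans no hypothesis tests, the PK table is descriptive and conditional on detection, and ADA is not among the minimum data for the escalation decision in SAP 3.1.3.

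**Conclusion.** The point holds for the participant-level status and for the PK-by-ADA table, and not for the by-visit endpoint. One kind of participant has positive status but no class, the classes that would separate new from pre-existing antibody are optional and unused in the listed outputs, and the PK table can therefore mix the two.

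The effect is conditional. It is zero if no active participant has pre-existing antibody that persists without a four-fold rise. Otherwise each such participant moves an ever-positive rate by 11.1 points in a dose group of nine, or 5.6 points across 18 active participants. These sizes assume full enrolment as planned and evaluable samples from everyone. The chance of meeting such a participant rests on an assumed prevalence that the documents do not supply. No planned incidence figure is shown to be wrong, and no bias in clearance has been demonstrated. What remains is an inexpensive improvement that would let the trial attribute antibody to the drug.

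**What to change.** Change the wording of SAP 3.2.6 and 4.12.1:

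- **Incidence.** Report treatment-emergent ADA (induced, plus boosted at four-fold or more) for each dose and for pooled placebo, beside the by-visit prevalence. Make the classification mandatory.
- **Missing class.** Add a class for pre-existing antibody that persists without a four-fold rise.
- **PK-by-ADA table.** State which status defines the rows, and show treatment-emergent positive, pre-existing not boosted, and negative separately. Where a row has fewer than three participants, list the individuals. Do not merge pre-existing positives with the negatives.
- **nAb.** The SAP specifies no nAb titre, so the four-fold rule cannot be applied. Separate participants by baseline nAb status instead.

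The cost is SAP text and table shells. The samples, assays, ADA titres and both class definitions are already in the plan. The price in presentation is smaller rows, some of which will be listings. If the SAP is already final, SAP Section 1 provides a form for recording the change.

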3.2.7 Pharmacokinetic Variables

Blood samples will be collected for XTMAB-16 PK analysis at pre dose (Hour 0), at 1 hour after the start of infusion, immediately after the 2-hour infusion (T; infusion termination), and at 3, 8, 14 hours on Day 1, and at 24 hours (Day 2), 50 hours (Day 3), 74 hours (Day 4), 170 hours (Week 2, Day 8), 338 hours (Week 3, Day 15), 674 hours (Week 4, Day 29), 1010 hours (Week 6, Day 43), 1346 hours (Week 8, Day 57), and 1682 hours (Week 10, Day 71) post infusion of XTMAB-16 or placebo. All sampling time points after time T refer to time from the start of infusion. Acceptable windows for PK sample collection are provided in Window Allowance Document. The exact time of sample collection must be recorded on the eCRF.

Unless otherwise stated, derivation of PK parameters will be the responsibility of Clinical Pharmacology, Modeling and Simulation (CPMS, formerly Quantitative Clinical Development (QCD), Parexel International. If calculable, the PK parameters listed in ([Table 2](#)) will be determined for XTMAB-16 in serum following single IV dose administration:

Table 2 Pharmacokinetic Parameters after Single Dose Administration

Parameter	Definition
C_T	XTMAB-16 serum concentration at the end of drug infusion
C_{max}	Maximum observed serum concentration determined directly from the concentration-time profile
t_{max}	Time of maximum serum concentration determined directly from the concentration-time profile
AUC_{0-inf}	Area under the concentration-time curve from time zero extrapolated to infinity
AUC_{0-last}	Area under the concentration-time curve up to last measurable concentration
λ_z	Terminal elimination rate constant
$t_{1/2}$	Terminal elimination half-life calculated as: $\ln 2/\lambda_z$

Parameter	Definition
CL	Total body clearance calculated as: Dose/AUC _{inf}
V _z	Volume of distribution during the terminal phase calculated as: Dose/($\lambda_z \cdot AUC_{0-\inf}$)
MRT	Mean residence time of the drug in the body
V _{ss}	Steady state volume of distribution following IV dosing calculated as: MRT·CL
DNC _{max} , DNAUC _{0-last} , DNAUC _{0-inf}	Dose-normalized C _{max} , AUC _{0-t} , and AUC _{0-inf}

Additional PK parameters may be calculated if needed.

